#### Confidentiality Statement

---

The confidential information in this document is provided to you as an investigator or consultant for review by you, your staff, and the applicable Institutional Review Board. Your acceptance of this document constitutes agreement that you will not disclose the information contained herein to others without written authorization from the sponsor.

The investigator will assess vADAS-Cog at baseline, 6, 12, 18, 24 weeks, 9 and 12 months, or upon termination of treatment. Testing sessions will include additional secondary psychological assessments including the National Institute on Aging's Alzheimer's Disease Cooperative Study-Clinical Global Impression Scale (ADCS-CGIC) by the clinician and patient/caregiver and the Alzheimer's Disease Cooperative Study-Activities of Daily Living (ADCS-ADL), Trail Making Test B, and ADAS-Cog. The ADCS-ADL, ADCS-CGIC, Logical Memory and Trail Making will be completed by blinded psychometricians.

Subjects will receive MRI brain scans at screening to ensure there is no existing exclusionary brain pathology. Brain pathology would include evidence of infection, infarction (including multiple lacunas in a critical memory structure), or other focal lesions. Central Reading of the MRIs will be conducted at Massachusetts General Hospital (MGH). Subjects who are re-screened for this study may utilize their initial screening MRI scan to determine eligibility if the initial screening MRI was completed within 90 days of re-screening. At 24 weeks and end of study (12 month), an MRI will assess changes in hippocampal volume, a biologic marker for AD. A repeat scan may be obtained if necessary. Additionally, as exploratory endpoints, subjects treated at selected sites will receive Transcranial Doppler or the Moor deep tissue oxygenation to evaluate cerebral blood flow at study start and periodically throughout the trial period.

Safety evaluation, including ongoing review of adverse events and vital signs will occur at every visit throughout the study. This trial will have frequent interim analyses to stop accrual early for expected success or for futility as outlined in more detail below.

For exploratory endpoints, blood samples will be drawn at screening, 12 weeks, 24 weeks and 12 months, or upon termination of treatment. A repeat lab draw may be obtained at any time if needed. Polymorphism of the apolipoprotein (ApoE) gene and its effect in modulating hippocampal change will be assessed at baseline. Additional exploratory lab endpoints include assessment of blood viscosity, inflammatory markers, and blood fibrinogen at baseline, 12 weeks, 24 weeks and 12 months, or upon termination of treatment. Exploratory endpoints of balance, functional mobility, and fall-risk will be measured via the Timed Up & Go (TUG) test and the Functional Reach Test at baseline, weeks 6, 12, 18, 24, 9 and 12 months, or upon termination of treatment. Neuro-behavioral symptoms will be assessed using the Neuropsychiatric Inventory (NPI) at baseline, weeks 6, 12, 18, 24, 9 and 12 months, or upon termination of treatment.

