## 5. STUDY DESIGN AND ENDPOINTS

### 5.1 Study Design

This pivotal, single blind, parallel design, multi-site study intends to examine the efficacy and safety of Renew™ NCP-5 therapy in the treatment of Cognitive Impairment due to Alzheimer's Disease or Mild Dementia of the Alzheimer's Type. Subjects will be prospectively randomized to treatment or active sham (in a 1:1 ratio) using stratification for Cognitive Impairment due to Alzheimer's Disease or Mild Dementia of the Alzheimer's Type, and CVR score at multiple sites. Subjects will be assessed for stratification and then randomized within strata to either the treatment group or active sham group with one treated subject for one active sham subject. Randomization assignments will be made using permuted blocks. Investigators shall receive the assignments from an Interactive Web Response System (IWRS). The following factors will be used for stratification prior to randomization: cognitive decline (MCI due to AD vs. mild AD) and CVR score (low/medium vs. high/very high).

Additional pre-specified subgroup analyses of the primary efficacy outcome will be conducted using the same method as the primary analysis. The subgroup includes cognitive decline (MCI due to AD vs. mild AD) and CVR score (low/medium vs. high/very high). These subgroup analyses results will not be used to draw conclusions of efficacy. The subgroup analyses will serve as a supportive purpose to the primary analysis; therefore, Type I error will not be adjusted for the subgroup analyses.

Prior to randomization, subjects will be diagnosed with either Cognitive Impairment due to Alzheimer's Disease or Mild Dementia of the Alzheimer's Type, based on the study checklist developed, which follows the 2011 National Institute on Aging (NIA)-Alzheimer's Association (AA) "core clinical criteria" guidelines. After the subject completes the MMSE2, LMII and the MOCA, the investigator will review the

---

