#### Confidentiality Statement

---

The confidential information in this document is provided to you as an investigator or consultant for review by you, your staff, and the applicable Institutional Review Board. Your acceptance of this document constitutes agreement that you will not disclose the information contained herein to others without written authorization from the sponsor.

results and complete the 2011 NIA-AA study checklist, which identifies the “core clinical criteria” for diagnosis of probable AD dementia as indicated by the presence of cognitive and/or behavioral symptoms. Positive responses to the first five questions are required for inclusion in the mild AD cohort. If the responses to the first five questions within the checklist for the diagnosis of probable AD dementia are not positive, the investigator will then complete the 2011 NIA-AA “core clinical criteria” study checklist for MCI due to AD. Responses to the first four questions of that study checklist for the diagnosis of MCI due to AD must be positive, and the clinical impression must conform with typical presentation of individuals for whom there is an intermediate level of certainty that they have MCI due to AD, in order for subjects to be included in the MCI due to AD cohort.

The MOCA, LM, MMSE2, and the complaint of memory loss by the subject and/or caregiver will be used to assess the subject; however, eligibility for the study will be determined by a MOCA score of greater than or equal to 11. The efficacy of Renew™ NCP-5 treatments to influence cognitive symptoms will be evaluated through performance on the vADAS-Cog compared to the active sham treatment group.

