#### 9.4 **Emergency procedure for unblinding**

For this study, the subject and the psychometrician/designee will be blinded. Neither the Renew™ NCP-5 operator nor the PI will be blinded. The psychometrician/designee administering all cognitive tests should be blinded. There does not seem to be any reason that the subject or psychometrician will be unblinded in the event of a serious adverse event. Only the investigator, who is unblinded, will need to assess what intervention the subject may need or whether the subject can continue in the study.

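### Section 5.1 gives the primary endpoint rating (vADAS-Cog) to the investigator, whom section 9.4 describes as unblinded

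*Protocol*

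**What the plan says.** Section 5.1 (Study Design) names a rater for vADAS-Cog and gives the schedule: "The investigator will assess vADAS-Cog at baseline, 6, 12, 18, 24 weeks, 9 and 12 months, or upon termination of treatment". Two sentences later, the same paragraph assigns other tests to a different role: "The ADCS-ADL, ADCS-CGIC, Logical Memory and Trail Making will be completed by blinded psychometricians". vADAS-Cog is not in that list.

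Section 9.4 (Emergency procedure for unblinding) sets out who is blinded: "For this study, the subject and the psychometrician/designee will be blinded". It continues that neither the device "operator nor the PI will be blinded". On serious adverse events it says: "Only the investigator, who is unblinded, will need to assess what intervention the subject may need". On testing it says: "The psychometrician/designee administering all cognitive tests should be blinded".

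Section 8.1 (Study Specific Procedures), under its heading on eligibility checks and cognitive assessments, fixes the order and timing of vADAS-Cog and states that psychometricians or their designees are blinded. It does not say in terms that they are the people who give vADAS-Cog. The visit descriptions in 8.4 list vADAS-Cog at each assessment without naming a rater.

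Section 5.2.1 makes vADAS-Cog the primary measure: the change from baseline, averaged over weeks 12, 18 and 24.

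**The concern.** The trial is single blind and the investigator knows the allocation. Blinding of the person who scores the outcome is therefore one of the main protections of the comparison with active sham. Section 5.1 read literally removes that protection for the primary endpoint, while keeping it for the four other tests listed in the same paragraph.

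Parts of the scale call for judgement. One of the examples of a 2-point change in 5.2.1 is a regrading of the severity of spoken-language difficulty, which a rater's expectation could influence.

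The same ratings feed more than the primary analysis. Section 5.2.2 derives the ADAS-Cog14 secondary endpoint from the vADAS-Cog subtests. Section 5.2.3 uses vADAS-Cog again for the payor-based comparisons at 24 weeks, 9 months and 12 months. Section 5.2.4 analyses two of its memory subtests. The primary endpoint also drives up to six interim looks for success or futility (sections 5.2.1 and 11), so a rating bias could affect stopping as well as the final result. It could not be removed after the data are collected.

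**Working it through.** This is mainly a comparison of text; the protocol states no figure to reproduce.

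**Step 1: who rates vADAS-Cog, and is that person blinded?**

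| Section | Rater | Blinding status |
|---|---|---|
| 5.1 | The investigator, named for vADAS-Cog | Unblinded, according to 9.4 |
| 9.4 | Psychometrician/designee, for all cognitive tests | Should be blinded |
| 8.1 | Psychometricians/designees, under the heading that covers vADAS-Cog | Blinded |
| 8.4 visit lists | None named | Not stated |

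The first two rows cannot both be followed. Sections 8.1 and 9.4 agree with each other, so 5.1 is the one out of line.

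**Step 2: does 5.1 use the word investigator loosely?** Elsewhere in 5.1 the investigator has a role distinct from giving tests: "After the subject completes the MMSE2, LMII and the MOCA, the investigator will review the" results, and, where the dementia checklist is not met, "the investigator will then complete the 2011 NIA-AA" checklist for mild cognitive impairment. There the investigator reads test results and makes the diagnosis. That use gives no reason to take the word as shorthand for the psychometrician.

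**Step 3: how many assessments are covered?** The 5.1 sentence lists baseline, weeks 6, 12, 18 and 24, and months 9 and 12.

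- Scheduled assessments: 7.
- After randomization: 7 − 1 = 6.
- In the primary endpoint (weeks 12, 18, 24): 3, all after randomization.

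Baseline is at Day −14 to Day −1, before allocation exists. Subtracting it cannot cancel a shift that depends on the arm and arises later.

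**Step 4: how would a shift carry through?** Suppose unblinded rating changes the arm difference by *d* points at each of the three visits, in a fraction *f* of subjects that is the same in both arms. Among affected subjects the endpoint shifts by (*d* + *d* + *d*)/3 = *d*. Over all subjects the arm difference shifts by *f* × *d*.

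The values below are assumptions, not protocol figures. The last column divides by the 2 points in 5.2.1.

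| *f* | *d* | Shift *f* × *d* | Share of 2 points |
|---|---|---|---|
| 0.25 | 0.5 | 0.125 | 6.25% |
| 0.25 | 1.0 | 0.25 | 12.5% |
| 1.0 | 0.5 | 0.5 | 25% |
| 1.0 | 1.0 | 1.0 | 50% |

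Where a site follows 9.4, its subjects are not in *f* and contribute no shift.

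**The case against.** The best defence is that the matter is already settled elsewhere. Section 9.4 is where the protocol sets out who is blinded, and it covers all cognitive tests, which must include vADAS-Cog. Section 8.1, the procedures section, agrees. On this view the 5.1 sentence is a statement of timing in a design overview, and saying that the investigator assesses a measure may mean only that the site is responsible for obtaining it. The missing entry in the list of blinded tests proves little, because that list also leaves out MMSE2, MOCA and NPI. The silence of the visit sections proves little either, since they name no rater for any cognitive test.

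Much of this stands. The intent is clear, the list is not exhaustive, and the visit sections are neutral. What the defence does not remove is that the Study Design section is the only place that names a rater for vADAS-Cog specifically. It does so in definite terms, while the sentence that would correct it sits under an emergency unblinding heading and is worded as a recommendation. Nothing says which section prevails.

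The objections to the size also have force. Neither *d* nor *f* is anchored in the protocol. The 50% end requires every subject to be rated unblinded. Several components are counts, so a uniform shift across the scale is not established. Section 5.2.1 describes the 2 points as an average change from baseline and does not call it a difference between arms, so the percentages give scale only. The conclusion does not rest on them.

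**Conclusion.** The contradiction is real and 5.1 is wrong as written: it assigns the primary endpoint measure to a person whom 9.4 describes as unblinded, at all 7 scheduled assessments, including all 3 that form the primary endpoint. This rests on the wording alone and needs no assumption about bias.

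The size of any effect on the result is unknown. It depends on how many sites act on 5.1 and how far knowledge of the allocation changes their scoring, and the protocol informs neither. The illustrative range is 0.125 to 1.0 point, with zero where sites follow 9.4. The correction is warranted because the primary endpoint is exposed, the damage could not be undone in analysis, and the remedy is small.

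**What to change.** In section 5.1, replace the sentence naming the investigator with: *A psychometrician or designee blinded to allocation will administer and score vADAS-Cog*, keeping the time points already listed. Add vADAS-Cog to the list, in the same paragraph, of tests completed by blinded psychometricians, so that 5.1, 8.1 and 9.4 agree. Brief all sites on the corrected sentence.

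A minor tidy-up in the same paragraph: ADCS-CGIC is described first as done by the clinician and the patient or caregiver, and then as completed by blinded psychometricians. The two descriptions should be aligned. They do not in themselves show any unblinded rating.

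The cost is one wording amendment and a site training note. No extra staff are needed, because 5.1, 8.1 and 9.4 already provide for blinded psychometricians. The design, schedule and analysis do not change.

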## 5.2 Endpoints

### 5.2.1 Primary Endpoint

The primary endpoint for this study is the **average of the change from baseline in vADAS-Cog score at 12, 18 and 24 weeks after initiation of treatment**. vADAS-Cog is an expanded version of the ADAS-Cog assessment, and the former has been shown to be a more sensitive measure of cognition than ADAS-Cog in subjects with vascular burden in the brain.

---

#### Confidentiality Statement

---

The confidential information in this document is provided to you as an investigator or consultant for review by you, your staff, and the applicable Institutional Review Board. Your acceptance of this document constitutes agreement that you will not disclose the information contained herein to others without written authorization from the sponsor.

The vADAS-Cog represents a collection of tests of different domains of brain function.

**A 2-point average change from baseline in vADAS-Cog at 12, 18 and 24 weeks after initiation of treatment will be used to determine effectiveness.** Examples of the typical functional changes associated with a 2-point change in vADAS-Cog include:

- Improvement in orientation – subject can now remember current date and day of week;
- Less errors in naming – 50% reduction in mistakes naming a real object;
- Improvement in following commands – subjects fail to follow 1/5 simple commands instead of 3/5 commands previously failed;
- Improvements in spoken language – misunderstanding decreases from moderately severe to mild (3-5 errors mean mild);
- Better constructional praxis – 40% improvement in number of figures copied correctly;
- Better word recall – 20% improvement in ability to remember words immediately after hearing them 3 times.

It is expected that the effect of the treatment will be demonstrated first at 12 weeks but will maintain or improve through to 24 weeks of treatment. Accordingly, since the 12 week (the completion of initial phase of treatment), 18 week and 24 week (end of maintenance phase) vADAS-Cog scores represent the entire expected period of the treatment duration, it is appropriate to measure the average of 12, 18 and 24 week vADAS-Cog scores as the primary endpoint for this study. The primary endpoint is the average of the change assessed at each of these three time points, referred to as an integrated primary endpoint.

Sponsor will repeat the analysis of the primary endpoint using 9-month and 12-month data.

As described in the Adaptive Design Report (ADR), included in Appendix A, the primary endpoint will be evaluated during interim analyses (after 100 subjects have been randomized and after every additional 25 subjects are randomized), up to a total of 250 subjects.

#### 5.2.2 Secondary safety and effectiveness endpoints

Because there is no gold standard to measure the changes from treatment in cognition for MCI or mild AD, secondary endpoints will include assessments performed in other similar studies. While cognitive and imaging assessments may show changes over time, it is important to assess the importance of change to the clinician and caregiver (ADCS-CGIC) and the ability of the subject to carry out activities of daily living (ADCS-ADL). The Trail Making Test B is used in many studies to assess executive function, a key to continued functioning for the patient. Because the vADAS-Cog includes the ADAS-Cog14 that has been used to assess changes in cognition in pharmaceutical studies, it is important to compare it to the findings from the vADAS-Cog.

---

#### Confidentiality Statement

---

The confidential information in this document is provided to you as an investigator or consultant for review by you, your staff, and the applicable Institutional Review Board. Your acceptance of this document constitutes agreement that you will not disclose the information contained herein to others without written authorization from the sponsor.

The secondary effectiveness endpoints of the study include:

- The safety of Renew™ NCP-5 treatments as reflected in adverse events, labs and vital signs;
- The average of the change from baseline in Alzheimer’s Disease Cooperative Study-Activities of Daily Living (**ADCS-ADL**) Total Score at 12, 18 and 24 weeks after initiation of treatment;
- The answers to the NIA’s Disease Cooperative Study-Clinical Global Impression of Change Scale (**ADCS-CGIC**) at 12, 18 and 24 weeks after initiation of treatment;
- The average of the change from baseline in executive function, assessed by the **Trail Making Test B** at 12, 18 and 24 weeks after initiation of treatment;
- The average of the change from baseline in **ADAS-Cog14** at 12, 18 and 24 weeks after initiation of treatment. ADAS-Cog14 score will be calculated using the subtests from the vADAS-Cog test and will not be conducted as a separate test.

Sponsor will repeat the analysis and conduct the battery of secondary endpoints on the 9 and 12 month data.

### 5.2.3 Payor-based endpoints

The payor-based endpoints, described below, will be used to assess the clinical and cost effectiveness of the Renew™ NCP-5 external counter-pulsation (ECP) for patients with Mild Cognitive Impairment due to Alzheimer’s Disease or Mild Dementia of the Alzheimer’s Type. Effectiveness of ECP on cognitive impairment, compared to active sham group, measured by the clinical effectiveness endpoints identified, will be key in communicating the value and benefits of adding ECP as a treatment option for this patient population. In order for physicians to widely access ECP as a treatment option for their patients, reimbursement from commercial payers will be required. To facilitate reimbursement, the study is measuring the impact of ECP on health related quality of life (HRQoL), reduction in disease burden, and health resource utilization (HRU) to help assess the cost effectiveness of ECP, and potential cost savings for health systems and payers. Results from this study will be presented to Centers for Medicare and Medicaid Services (CMS) and commercial insurers to initiate reimbursement approval of ECP.

- A comparative analysis between treatment and active sham groups on **Health Resource Utilization (HRU) data** will be conducted using the following analysis and time points:
  - The difference in change from baseline analyzed at:
    - 24 weeks
    - 9 months
    - 12 months
  - An average of 24 weeks, 9 months, and 12 months

---

#### Confidentiality Statement

---

The confidential information in this document is provided to you as an investigator or consultant for review by you, your staff, and the applicable Institutional Review Board. Your acceptance of this document constitutes agreement that you will not disclose the information contained herein to others without written authorization from the sponsor.

- A comparative analysis between treatment and active sham groups in their change of ability to drive based on a self-rated answer to a question
- A comparative analysis between treatment and active sham groups in **vADAS Cog Scores** will be conducted using the following analysis and time points:
  - The difference in change from baseline analyzed at:
    - 24 weeks,
    - 9 months,
    - 12 months;
  - An average of 24 weeks, 9 months, and 12 months
- A comparative analysis between treatment and active sham groups in **ADCS-ADL Scores** will be conducted using the following analysis and time points:
  - The difference in change from baseline analyzed at:
    - 24 weeks
    - 9 months
    - 12 months
  - An average of 24 weeks, 9 months, and 12 months
- A comparative analysis between treatment and active sham groups in **Fall Risk Assessment/Functional Reach Test/TUG Test Scores** will be conducted using the following analysis and time points:
  - The difference in change from baseline analyzed at:
    - 24 weeks
    - 9 months
    - 12 months
  - An average of 24 weeks, 9 months, and 12 months
- A comparative analysis between treatment and active sham groups in **NPI Aggression Index Scores** will be conducted using the following analysis and time points:
  - The difference in change from baseline analyzed at:
    - 24 weeks
    - 9 months
    - 12 months
  - An average of 24 weeks, 9 months, and 12 months
- The answers to the **QOL/Patient Survey** at 12 months after initiation of treatment.

#### 5.2.4 Exploratory endpoints

Imaging studies may be important in understanding the mechanism by which treatment results in change in cognition or delays the progression of the disease. Understanding that there is a vascular component to MCI and mild AD, assessing changes in cerebral blood flow can inform the mechanism of change. Research indicates that hippocampal volume change over time, measured by MRI, has potential as a marker for MCI and AD. MRI will be conducted at screening after all other assessments have found

---

